	

ii. Wound infection (y/n)

c. Length of stay (days; typically 0 to 1)

i. Discharge date/time (m-d-y; hh:mm)

3. Use of postoperative pain medication

a. Opioids (y/n for each: fentanyl, Dilaudid, oxycodone, Norco, tramadol, Percocet, Demerol)

i. Morphine equivalents (MME)

b. Non-opioids (y/n for each: Toradol, Tylenol, oxybutynin)

4. Postoperative pain scores (0-10; asleep, missed, or discharged)

a. Average and maximum scores during each interval (during the PACU stay, the first 4 hours on the floor, next 8 hours, and the following 8 hours; as well as the final score immediately prior to discharge)

b. At each location (abdomen, legs, groin, scrotum, shoulder, other/specify)

5. Timing of ability to pass gas (day 0, day 1, day 2, >day 2)

6. Clinically-significant ileus (i.e., requiring treatment; y/n)

Follow-Up (1 week, 1 month, & 3 months)	

1. QoR-15 (0-150) – only asked at week 1

a. Collected (y/n)

b. Score (0-150)

2. Prescription(s) given (y/n) – only asked at week 1

a. Prescription(s) filled (y/n)

b. Opioids (y/n for each: fentanyl, Dilaudid, oxycodone, Norco, tramadol, Percocet)

i. Number of pills taken for each (#)

ii. Morphine equivalents (MME)

c. Non-opioids (y/n for each: Toradol, Tylenol, oxybutynin)

3. Scrotal swelling (y/n) – only asked at week 1

4. Leg weakness (y/n)

a. Left, right, bilateral

b. Degree of weakness (each leg; mild, moderate, severe)

c. Impaired ability to walk

d. Impaired ability to drive

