We will collect information on pertinent surgical outcomes that occur through discharge. The average amount of time spent in the PACU is roughly 1-2 hours, and the average hospital length of stay is 0-1 days. For Intraoperative Item #2, a deviation from the standard port number/size(s)/locations would be due to body habitus, and will not have an effect on clinical outcomes. For Intraoperative Item #3, continuous values will be exported into individual patient-specific Excel spreadsheets with the assistance of the CareConnect Systems Analysts. This is due to the fact that there are far too many data points (8 different variables every 1 minute for 120 minutes) to be manually extracted and subsequently manually entered. The PI will perform individual analyses on these data sets in conjunction with Analysts, and

calculate means and standard deviations to be entered into REDCap. For Intraoperative Item #15, we are collecting whether the obturator artery was affected for each leg, as this could potentially be a confounder to postoperative leg pain (i.e., increased pain in the affected leg). Finally, the presence of wound infection (in the PACU and on the Floor; Postoperative Items #1b-iii and #2b-iii, respectively), as well as clinically-significant ileus (on the Floor; Postoperative Item #6) will be evaluated and assessed by nursing staff per routine care and entered into the medical record.

The Quality of Recovery (QoR)-15 questionnaire (Appendix E) is used to evaluate recovery from anesthesia. The tool consists of 15 questions that assess patient-reported quality of postoperative recovery using an 11-point (i.e., 0-10) numerical rating scale, where "0" refers to "all of the time [poor]" and "10" refers to "none of the time [excellent]." Therefore, a higher score refers to better quality of recovery. The questionnaire assesses basic and essential activities of daily life (ADLs), pain, emotions, and personal/overall well-being, among others. The survey will be administered at the 1-week follow-up visit only, and takes approximately 2-3 minutes to complete.

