**Table 2. Post-operative pain monitoring schedule.**

Timeframe	Description	Time-Points	Pain Locations
During PACU stay	Upon admission to the PACU (typical stay of 1-2 hours)	PACU	Abdomen Legs
1 st 4 hours on the floor	Every 2 hours during the first 4 hours on the floor	Floor-0, 2, & 4 (hours 0 through 4)	Groin Scrotum
Next 8 hours on the floor	Every 2 hours during the next 8 hours on the floor	Floor-6, 8, 10, & 12 (hours 5 through 12)	Shoulder
Following 8 hours on the floor	Every 2 hours during the following 8 hours on the floor	Floor-14, 16, 18, & 20 (hours 13 through 20)	Other/specify
Final score immediately prior to discharge	Recorded on the floor prior to discharge; OR via phone call by CRC for those discharged same-day	Discharge, or Post-discharge	

1-Scores measured only while inpatient (or post-discharge for those discharged same-day) and awake; measures not taken in <1 hour from planned time will be marked as "missed."

Pain scores are measured using an 11-point numerical rating scale (NRS), in which a rating of 0 corresponds to no pain, 1-3 indicates mild pain, 4-6 indicates moderate pain, and 7-10 corresponds to severe pain. Scores are recorded by nursing staff as part of routine care in the PACU and on the postoperative recovery floor during the inpatient stay, however these measures are often not recorded in a consistent fashion with respect to timing. Therefore, we will record scores every 2 hours during the inpatient stay while the patient is awake (with the exception of the PACU, which occurs only at admission), and determine the average and maximum scores reported over sequential timeframes: during the PACU stay (typical stay of 1-2 hours), the first 4 hours on the floor, next 8 hours, and the following 8 hours; as well as the final score immediately prior to discharge (see Table 2). There will be no strict time window due to the variability of sleep schedules and discharge timing during the short inpatient stay, however, scores will be marked as "missed" if not recorded in <1 hour of the planned time. Pain will be measured with respect to the abdomen, legs, groin, scrotum, shoulder (due to insufflation), and "other" location. Pain medication morphine equivalents (MME) will also be measured over the same sequential timeframes during the inpatient stay through 1 week postoperatively. Patients

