will be educated on the importance of bringing all medications to follow-up visits, which will lead to more accurate pain medication counts and calculations.

Patients are typically discharged on Day 0-1, and for those discharged on Day 0 (i.e., same-day), the CRC will call the following morning to evaluate pain (see Appendix C). Because we are targeting same-day or next-day discharge, there is the potential for missing data in the first 24-hour period. Therefore, there will be no restrictions or protocol deviations for pain scores, as we are collecting scores only while inpatient/awake and via phone call for those discharged same-day. Follow-up visits per routine care occur at approximately 1 week postoperatively for catheter removal, as well as at 1 month and 3 months. Appointments will follow routine scheduling practices for the office, which may include variance in exact visit timing. Generally, patients will have 1 week postoperative visit around 5-7 days after surgery, but may be delayed further by approximately 1 week depending on scheduling availability and/or clinical indication (e.g. need for cystogram). Follow-up visits are generally 1 month and 3 months post-surgery, but may occur approximately a couple weeks before or after as per physician standard of care scheduling to accommodate patient and physician availability. There will be no strict visit windows to allow for visit scheduling flexibility. Because the majority of RALP patients will be eligible for participation, schedulers will be educated on the importance of return visit timing accuracy. There will be no extended or long-term follow-up via direct patient contact or EMR review.

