## 2.4 – Statistical Analysis

The demographic and clinical characteristics of male patients age 18 or older with prostate cancer who are eligible and electing to undergo robotic assisted laparoscopic prostatectomy (RALP) at OhioHealth Dublin Methodist Hospital (DMH) Robotic Urology with the Principal Investigator will be reported using means and standard deviations or medians and interquartile ranges for continuous variables, or frequencies and percentages for categorical variables. We plan to compare the clinical outcomes of patients between different insufflation pressures (6 versus 15 mmHg). Continuous variables will be compared between two groups using independent sample t-test or Mann-Whitney U test, as appropriate, and categorical variables will be compared using Chi-square test or Fisher's exact test, as appropriate.

During the previous feasibility study of RALPs at an insufflation pressure of 6 mmHg, we found that there was a significant difference in pain scores at 5-12 hours. The average score in the 6 mmHg group was 3.2, and that in 15 mmHg historical group was 3.9. Using these values and an assumed standard deviation within each group of 1.4 (effect size = 0.5), at a significance level of 0.05 to achieve 90% power, the estimated sample size will be 86 patients in each group (total 172 patients). However, to account for ineligible patients after enrollment (estimated 10%), we will enroll minimum of 192 patients.

**Aim #1) Compare average postoperative pain medication use between groups, as measured in total morphine equivalents (MME) over time at pre-specified time intervals through follow-up at 1 week.**

Postoperative medication use between the two groups will be assessed at the following time points: during the PACU stay, during the first 4 hours on the floor, next 8 hours, the following 8 hours, and following discharge through the 1-week follow-up visit. Both total and average medication use measured in total morphine equivalents at/during each time point will be calculated and compared between two groups (6 versus 15 mmHg) using independent sample t-test or Mann-Whitney U test, as appropriate.

**Aim #2) Compare average and maximum postoperative pain scores between groups, as measured using the self-reported 11-point numerical rating scale (NRS), over time at pre-specified time intervals through discharge.**

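### The post-discharge opioid count and the QoR-15 close at a visit that can fall from about day 5 to about day 14, so patients are compared over unequal periods and at different recovery stages

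*Combined protocol and SAP*

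**What the plan says.** Section 2.3 (Study Design, text after Table 2) states that "patients will have 1 week postoperative visit around 5-7 days after surgery, but may be delayed further by approximately 1 week". The reasons given are scheduling availability and clinical indication, with the need for a cystogram as the example. It adds: "There will be no strict visit windows to allow for visit scheduling flexibility". The safeguard on timing is that schedulers will be taught why accurate return visits matter.

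Two definitions of the opioid period stand side by side. Section 2.4, Aim #1, takes the last interval as "following discharge through the 1-week follow-up visit". Section 2.3, below Table 2, says: "Pain medication morphine equivalents (MME) will also be measured over the same sequential timeframes during the inpatient stay through 1 week postoperatively". The wording of Aim #1 in Section 1.2 can be read either way.

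Post-discharge use is captured in Table 1 (Follow-Up) as "Number of pills taken for each", converted to MME. Table 1 lists no dates of use. To support the count, patients "will be educated on the importance of bringing all medications to follow-up visits". Section 2.4 compares total and average MME per interval by t-test or Mann-Whitney U test and does not define the divisor of the average. The regression described under Aim #2 names demographic and clinical characteristics, not visit day or interval length.

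For the QoR-15, Section 2.2 says: "The survey will be administered at the 1-week follow-up visit only".

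**The concern.** A cumulative count grows with the time over which it is taken. If the interval closes at a visit that moves by more than a week, a patient seen on day 5 and one seen on day 14 contribute different quantities under the same label. The two definitions also cannot both be met. A day-14 count runs a week past one week, and a day-5 visit closes before one week is reached. The QoR-15 has the same problem in another form, because recovery on day 5 is not the same state as recovery on day 14.

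What is at stake is the precision and meaning of the post-discharge opioid comparison. With discharge usually on day 0 or 1, that interval covers most of the first week.

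**Working it through.** **The plan's own figure.** The only sample size in the plan rests on pain scores at 5-12 hours: means 3.2 and 3.9, SD 1.4, so d = 0.7/1.4 = 0.5, with alpha 0.05 (two-sided assumed) and power 90%. The normal approximation gives n = 2(1.960 + 1.282)²/0.5² = 84.1, so 85 per group. The t-test solution is 85.03, so 86, as stated. Then 172/0.90 = 191.1, so 192. The figure reproduces, and visit timing does not affect it. The plan gives no figure for the last MME interval or for the QoR-15.

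**Range of visit days (Section 2.3).** Earliest usual visit: about day 5. Latest usual visit plus the allowed delay: 7 + 7 = about day 14. Counted from surgery the ratio is 14/5 = 2.8. The interval starts at discharge, so with discharge on day 1 it is 13/4 = 3.25.

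**Effect on one patient's count (illustration).** The documents give no rate of opioid use, so the rate is an assumption. If daily use halves every h days and discharge is on day d, the count to day b relative to the count to day a is

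ratio = (1 − 2^(−(b−d)/h)) / (1 − 2^(−(a−d)/h)).

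For h = 2, d = 1, b = 14, a = 5: (1 − 2^(−6.5))/(1 − 2^(−2)) = 0.989/0.750 = 1.32.

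| Assumed daily use | Discharge day 0, day 14 vs 5 | Discharge day 1, day 14 vs 5 | Discharge day 1, day 14 vs 7 |
|---|---|---|---|
| halves every day | 1.03 | 1.07 | 1.02 |
| halves every 2 days | 1.21 | 1.32 | 1.13 |
| halves every 3 days | 1.40 | 1.58 | 1.27 |
| halves every 5 days | 1.71 | 1.96 | 1.48 |
| constant | 2.80 | 3.25 | 2.17 |

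The last column is the gentler contrast: the same day-7 visit, on time or a week late.

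**Spread of visit day across patients.** The share of delayed visits, p, is not given. Take on-time visits at day 6 and delayed ones at day 13 (6 + 7). Then mean = 6(1 − p) + 13p and SD = 7√(p(1 − p)).

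- p = 10%: mean 6.7 days, SD 2.1
- p = 20%: mean 7.4 days, SD 2.8
- p = 50%: mean 9.5 days, SD 3.5

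The documents give no between-patient spread of MME, so this cannot be turned into a loss of power.

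**What bias would require.** If the share of delayed visits differed between arms by 5, 10 or 20 percentage points (assumed), the mean interval would differ by 7 × 0.05 = 0.35, 7 × 0.10 = 0.7 or 7 × 0.20 = 1.4 days. Where use is falling, these late days add less opioid than the same number of early days.

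**The case against.** The strongest defence is that the variation is disclosed, has a practical reason and is partly managed through scheduler education. Allocation is randomized 1:1, so delay due purely to scheduling should balance between arms. All of that stands, and it is why the expected effect is noise. Education cannot, however, prevent a delay made for a clinical reason.

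A reader might go further and infer that the opioid or QoR-15 result will be biased towards one arm. The documents do not support this. Clinically indicated delay could differ by arm: Section 1.1 mentions perceived concerns about visibility and hemostasis at low pressure, and the operating surgeon knows the assigned pressure. But no rate of delay or of cystograms is given, overall or by arm. Nor can a direction be assumed for the QoR-15. Later completion might raise scores, while patients delayed for a clinical reason might score lower.

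A reader might also take 2.8 or 3.25 as the size of a distortion in the trial result. Each contrasts two extreme visit days at constant use. If use falls quickly the ratio is close to 1.

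Three further limits stand. Only one of five Aim 1 intervals is touched, and the QoR-15 appears in no aim and is not named in Section 2.4. The Follow-Up form (Appendix D) is not reproduced in the text reviewed, so it cannot be said that no visit date is recorded; the medical record may also supply one. And if average MME means per day, it would partly correct for interval length. The plan does not say so, total MME would remain affected, and a per-day rate does not equalize periods when use declines.

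**Conclusion.** The point holds as a limited design weakness. As written, post-discharge MME is compared over periods that end anywhere from about day 5 to about day 14. Sections 2.3 and 2.4 define the end of that period differently, and nothing in the stated analysis accounts for the difference. The QoR-15 is likewise taken at different recovery stages.

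The expected consequence is added noise in this one interval and in the QoR-15. Its size depends on how fast opioid use declines and how many visits are delayed, and the documents give neither. Between-arm bias is possible but not shown. The four earlier MME intervals, inpatient pain scores, tidal volume, length of stay and the sample size are unaffected. This is a worthwhile, cheap improvement and does not undermine the trial.

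**What to change.** Leave visit scheduling as it is and fix the outcome period.

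- **Reconcile the definitions.** Make Sections 1.2, 2.3 and 2.4 give the same end point for the last MME interval.
- **Opioid count.** On the Follow-Up form (Appendix D), record the visit date, the date of the last opioid pill, and pills taken through a fixed day that essentially every visit covers. An example is the end of postoperative day 4, the last full day before the earliest usual visit. A day-5 cut-off would not work, because a patient seen on day 5 has not completed that day. A pill-diary line on the discharge sheet would support the count.
- **Analysis.** Define Aim 1's final interval as discharge through that fixed day, and report the total through the visit as a secondary result.
- **QoR-15.** Keep it at the visit and record the completion day. Add a sensitivity analysis restricted to visits on days 5-7 or adjusted for completion day. Visit day arises after randomization, so this analysis is supportive only.

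The cost is a few form fields, a diary line and a few sentences in the plan, with no extra visit or call. Late-visit patients must recall some use by day, and later opioid use moves to the secondary comparison. The start of the interval will still vary with discharge day, which this change does not address. It has to be made prospectively, because an undated pill count cannot be divided by day afterwards.

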**Table 3. Study Calendar.**

	Baseline	Surgery & Post-Op Stay	Days 1 & 2 (post-discharge)	1-Week Follow-up	1-Month Follow-up	3-Month Follow-up
Informed Consent	x					
Randomization		x				
Office Visit	x			x	x	x
Intra- & Post-Op DCF		x				

(Appendices A&B)						
Post-Discharge DCF (Appendix C)			x*			
Follow-Up DCF (Appendix D)				x	x	x
QoR-15 (Appendix E)				x		
Phone Calls			x			

\* Patients will be called for pain scores on day 1 if discharged same day; patients will be called on days 1 & 2 to assess the ability to pass gas.

We do not expect any treatment-related adverse events (AEs) or excess risk associated with randomization to the study group, as all surgical procedures are considered routine care. Therefore, we will not be tracking treatment-related AEs, only treatment-related serious adverse events (SAEs), which will be reported to the OhioHealth IRB via IRBNet reporting using the Adverse Event Template Form, per institutional and national guidelines, within 10 business days of discovery or notification of the event. SAEs will be tracked for 90 days following discharge via chart review. Patients will be removed from the study only if they revoke their informed consent prior to surgery. There are no intraoperative events that would warrant study removal, and changes in insufflation pressure will be recorded intraoperatively as mentioned above. Further, patients who do not return for follow-up visits (which is not anticipated in this population) will still be analyzed in the final dataset.

Only de-identified or non-identifiable data will be reported in the study. Only the IRB-approved study staff will have access to patient information. All resulting data will be stored in electronic format; electronic files will be stored on a password-protected computer and paper files will be stored in a secure facility with limited access (the offices of the OhioHealth Research Institute). Participants will not be excluded on sexual orientation, socioeconomic, racial, or religious identity. The data collection and storage processes will follow HIPAA guidelines in accordance with 21 CFR 46.115 (b): to protect both confidentiality and privacy of each participant. All PHI data will be released or destroyed per institution protocol.

The only potential risk associated with this study is loss of confidentiality, which will be minimized by limiting access to data and de-identifying data at study completion. The information from this study will be used to identify opportunities to improve the care of our patients by potentially encouraging surgeons performing all types of laparoscopy or robotic surgery to use lower pressures, in compliance with current recommended evidence-based practice guidelines for our patients at OhioHealth. Potential patient benefits to a lower pneumoperitoneal insufflation pressure include decreased postoperative pain and improved intraoperative ventilation. As this study meets the FDAAA 801 definition of an "Applicable Clinical Trial", it is required that the study be registered on ClinicalTrials.gov. The PI will register and activate the study account prior to enrollment, and all results will be entered upon study completion, following statistical analysis, per the Results Database Guidelines.

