We plan to examine the impact of low pressure during RALP with the intention of identifying whether lower pressures might benefit patients. We hypothesize that a low insufflation pressure may provide an improvement in postoperative pain and abdominal distension in addition to potential physiologic benefits, and that these factors might then allow a shorter hospital stay. We previously initiated a protocol in September of 2016 (IRB# 1066864) to perform RALPs at an insufflation pressure of 6 mmHg with the intention of increasing the pressure as needed on an individual patient level. In order to determine whether this might allow earlier discharge when successful, we began allowing for same-day discharge in patients meeting appropriate criteria. Having now demonstrated feasibility in over 300 consecutive patients using this ultralow pneumoperitoneum protocol, we now plan to conduct a randomized trial to compare a pressure of 6 mmHg with patients having RALP at a standard pressure of 15mmHg to determine whether there is a true benefit.

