### **2.3 – Study Design**

We propose a prospective, randomized, controlled trial comparing insufflation pressures during RALP. Standard pressure is typically 15 mmHg, while in our previous study we determined that 6 mmHg is possible routinely; therefore, we plan to compare the clinical outcomes of patients between pneumoperitoneal pressures. Potential study subjects will be identified by reviewing clinic schedules at the PI's Robotic Urology practice at Dublin Methodist Hospital. As part of the new patient paperwork, patients will be mailed an informational letter (see Appendix G) highlighting active research studies for review prior to the index routine visit with the PI.

All patients that are candidates for RALP will be screened by the Clinical Research Coordinator (CRC) prior to their surgery planning visit. Once a patient is identified as meeting all study criteria, they will be approached by the CRC at their visit and the study will be thoroughly explained. After the patient has had all their questions answered and has agreed to participate in the study, informed consent will be obtained, followed by randomization in a 1:1 single-blinded fashion to either a pneumoperitoneal insufflation pressure of 15 mmHg (control group) or 6 mmHg (study group). The randomization allocation schedule will be developed by staff from the OhioHealth Research & Innovation Institute (OHRI), and will be hidden from the investigators until directly prior to surgery to prevent bias. Specifically, the CRC will open the randomization envelope in the operating room (OR) immediately prior to surgery. Randomization will be blocked to prevent selection and accidental bias.

Patients will be prepared for surgery per standard institutional policy and routine practice; the only difference in surgical technique will be the insufflation pressure applied. All ports will be placed

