according to routine care using the AirSeal iFS, and all clinical decisions will be made per standard practice and policy. [name] (the PI) will be the only surgeon performing these procedures, eliminating any variation in technique between surgeons. Participants in this study are not exposed to any additional or different risks associated with the surgery, as all patients will undergo insufflation. Following trocar placement, initial insufflation will be performed at 6 mmHg for patients in the study group and 15 mmHg for patients in the control group. If required, insufflation pressures for the study group will be increased up to 15mmHg per standard surgeon protocol. Increased insufflation pressure will be maintained either transiently (≤5 minutes to control bleeding or to improve access/visualization) or for the duration of the procedure as per surgeon need. The amount of time at each insufflation pressure will be recorded.

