**Aim #4) Compare average length of stay (typically 0-1 days) between groups.**

The average length of stay postoperatively will be compared between the two groups using independent sample t-test or Mann-Whitney U test, as appropriate. Also, the proportion of patients in each group who went home on day 1 versus day 0 will be compared using Chi-square test or Fisher's exact test, as appropriate. A difference of 10% in the proportion of patients will be considered clinically significant.

A p-value of less than 0.05 will be considered statistically significant for analysis. All of the analyses will be performed using SAS Enterprise Guide, version 7.1 (SAS Institute, Cary, NC).

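### Only treatment-related SAEs are tracked, no relatedness assessor or blinding of that judgement is stated, and section 2.4 names no SAE summary by arm

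*Combined protocol and SAP*

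**What the plan says.** The safety rule is in section 2.3, in the text below Table 3. After stating that no treatment-related adverse events or excess risk are expected in the study group, it says: "Therefore, we will not be tracking treatment-related AEs, only treatment-related serious adverse events (SAEs". These events go to the IRB within 10 business days. A tracking window follows: "SAEs will be tracked for 90 days following discharge via chart review". That sentence does not repeat the treatment-related qualifier.

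On knowledge of the arm, section 2.3 calls the trial single-blinded without naming the blinded party. Allocation is hidden from the investigators until just before the operation, when "the CRC will open the randomization envelope in the operating room (OR) immediately prior to surgery". The principal investigator "will be the only surgeon performing these procedures" and adjusts the insufflation pressure during them.

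Table 1 (section 2.2) lists no SAE, readmission, reoperation or transfusion variable. It does list, for both arms and with no relatedness condition:

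- estimated blood loss, pressure increases, loss of pneumoperitoneum and surgical margins;
- wound infection in the PACU and on the floor, and clinically significant ileus;
- scrotal swelling at week 1, and leg weakness at follow-up.

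Of wound infection and ileus, section 2.2 says that they "will be evaluated and assessed by nursing staff per routine care and entered into the medical record".

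Section 2.4 opens its comparisons with a general statement: "We plan to compare the clinical outcomes of patients between different insufflation pressures (6 versus 15 mmHg". It then covers baseline characteristics, opioid use, pain scores, tidal volume and length of stay. It does not mention SAEs.

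**The concern.** In a randomised comparison, serious events need no case-by-case attribution if all of them are counted in both arms. A rule that keeps only treatment-related events gives up that protection. It makes inclusion depend on a judgement, here with no named judge, no criteria and no stated blinding, in a protocol that already expects no such events.

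Timing makes this relevant to this trial. The Background argues that low pressure may reduce pain and distension, "and that these factors might then allow a shorter hospital stay", and Aim #4 compares day-0 with day-1 discharge. If the low-pressure arm does leave earlier, more of its course falls outside inpatient recording, where the SAE rule is the main planned route for other serious events. Readmission, the natural counterpart of earlier discharge, is not a listed variable. Section 2.3 also hopes that the findings will encourage lower pressures across laparoscopic and robotic surgery, so readers will look for a plain account of serious events in each arm.

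**Working it through.** **1. Scope of the rule.** The first sentence defines a class (treatment-related SAEs) and its reporting route. The second gives a duration and a source for SAEs. The abbreviation most naturally refers back to the class just defined, so the second sentence adds a window and not a second scope. It can also be read as all SAEs. Two abstractors could follow the text in good faith and build different datasets.

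**2. Who decides.** No section names a relatedness assessor, gives criteria, or says whether the assessor is blind. The text establishes only that the coordinator and the surgeon know the arm. That either of them would make the judgement is an inference.

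**3. What is captured without the filter.**

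| Event | Where recorded | Relatedness filter |
|---|---|---|
| Blood loss, pressure changes, margins | Table 1, intraoperative | No |
| Wound infection | Table 1, PACU and floor | No |
| Clinically significant ileus | Table 1, postoperative | No |
| Scrotal swelling, leg weakness | Table 1, follow-up | No |
| Other SAEs | Section 2.3, 90-day chart review | Yes, on the natural reading |
| Readmission, reoperation, transfusion | Not listed; only if they count as a tracked SAE | Yes, on the natural reading |

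The remaining gap is other serious events, mainly after discharge.

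**4. Arm sizes.** The plan's own figures reproduce. A difference of 3.9 − 3.2 = 0.7 with SD 1.4 gives an effect size of 0.5. A two-sided t-test at 0.05 with 90% power needs 85.03, so 86 per arm, or 172 in total. Then 172/0.9 = 191.1, so 192 are enrolled, 96 per arm. This point does not dispute the sample size.

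**5. What a table by arm could show.** The documents give no SAE rate, so the rates below are assumptions. With a common rate p and n per arm, the 95% CI half-width for the difference is 1.96 × √(2p(1−p)/n). For p = 0.05 and n = 96 this is 1.96 × √(0.095/96) = 0.0617.

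| Assumed rate | n = 96 | n = 86 |
|---|---|---|
| 5% | 6.2 points | 6.5 points |
| 10% | 8.5 points | 9.0 points |
| 15% | 10.1 points | 10.7 points |

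For 5% against 10%, the half-width is 1.96 × √((0.05×0.95 + 0.10×0.90)/n), which is 7.4 points at 96 and 7.8 at 86. The power of Fisher's exact test at two-sided 0.05, by enumeration of both binomials, is 18% at 96 and 16% at 86. A table by arm can therefore only be descriptive. These figures measure the precision of the remedy. They do not measure how many events the filter would lose, which cannot be computed from the documents.

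**The case against.** The best defence is that the plan is not silent on harm. Several complications are recorded without a filter. Patients discharged the same day are called the next morning, calls about passing gas are repeated if needed, and visits at 1 week, 1 month and 3 months have their own form. The Adverse Event Template Form and the appendix forms were not supplied and may hold a relatedness field. The institutional and national guidelines cited for SAE reporting may supply a definition. Section 2.3 also commits to entering all results in the trial registry under its guidelines. Most of this stands and limits the gap. It does not close it, because the listed content of the calls and visits does not include readmission, reoperation or general SAEs, and a general sentence on comparing outcomes cannot recover events that were never recorded.

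Three stronger readings may tempt a reader, and the documents do not support them:

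- **The two SAE sentences contradict each other.** They are ambiguous; the second most naturally refers back to the first.
- **The trial's SAE comparison is biased.** Section 2.4 names no such comparison. Bias would arise only if serious events were later compared by arm from filtered data.
- **A known share of patients will move out of inpatient recording.** Section 2.4 says of discharge day: "A difference of 10% in the proportion of patients will be considered clinically significant". Ten per cent of 96 is 9.6 patients, but this is a threshold for importance and not an expected effect.

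**Conclusion.** The point holds in a limited form. On its natural reading, section 2.3 lets attribution decide whether an SAE is tracked, without naming the assessor or stating that the assessor is blind, while the surgeon and the coordinator know the arm. SAEs, readmission, reoperation and transfusion are absent from Table 1, and section 2.4 plans no SAE summary by arm. What is exposed is the completeness of serious-event data, mainly after discharge. No aim, primary comparison or sample size is affected.

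The size and direction of any bias cannot be derived. The conclusion rests on the supplied text alone, and a relatedness field or definition in the missing forms would narrow it further. The change is worth making because it is cheap and the chart review is already planned.

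**What to change.** **Section 2.3, safety text below Table 3.** State that all SAEs, as defined by the institutional and national guidelines already cited, are recorded in both arms from surgery through the 90-day post-discharge chart review, regardless of attribution. Record relatedness as a separate field with a named assessor, blind to arm where existing staff allow. Add unplanned readmission, reoperation and transfusion as separate yes/no fields, without declaring each of them an SAE. Leave IRB reporting of treatment-related SAEs unchanged.

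**Section 2.4.** Add that the number of patients with at least one SAE, and the numbers with readmission or reoperation, are reported descriptively by randomised arm with the between-arm difference and 95% CI. State that a non-significant difference is not evidence of equal safety.

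**Cost.** A wording amendment, a few fields in a review already planned, one table and modest abstraction time. The estimates will be imprecise, as shown above, and cannot establish equal safety.
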